4.2.2 Rationale for Dose Selection/Regimen/Modification

4.2.2.1 Rationale for Dose Selection / Regimen for the Experimental Arm

The following dose regimen is selected for the axitinib/pembrolizumab combination:

- Axitinib 5 mg BID dosed continuously
- Pembrolizumab 200 mg Q3W

In the Phase Ib study KN035 (A4061079) that evaluated the combination of axitinib and pembrolizumab, axitinib 5 mg BID continuous dosing and pembrolizumab 2 mg/kg Q3W was determined as the recommended combination regimen (see Section 4.2.1). However, based on collective evidence, a flat dose of 200 mg Q3W has been determined for pembrolizumab used either as monotherapy or in combination regimens.

Rationale for using 200 mg Q3W dose for pembrolizumab

The dose of pembrolizumab planned to be studied in this trial is 200 mg Q3W. The dose recently approved in the US and several other countries for treatment of melanoma is 2 mg/kg Q3W. Information on the rationale for selecting a 200 mg Q3W dose is summarized below.

An integrated body of evidence suggests that 200 mg Q3W is expected to provide similar response to 2 mg/kg Q3W, 10 mg/kg Q3W, and 10 mg/kg Q2W. Previously, a flat pembrolizumab exposure-response relationship for efficacy and safety has been found in subjects with melanoma and NSCLC in the range of doses between 2 mg/kg and 10 mg/kg. Exposures for 200 mg Q3W are expected to lie within this range and will be close to those obtained with the 2 mg/kg Q3W dose.

A population PK model, which characterized the influence of body weight and other patient covariates on exposure, has been developed. The PK profile of pembrolizumab is consistent with that of other humanized monoclonal antibodies, which typically have a low clearance and a limited volume of distribution. The distribution of exposures from the 200 mg fixed dose are predicted to considerably overlap with those obtained from the 2 mg/kg dose and importantly will maintain individual patient exposures within the exposure range established in melanoma and NSCLC as associated with maximal clinical response.

In translating to other solid tumor indications, similarly flat exposure-response relationships for efficacy and safety as observed in subjects with melanoma and NSCLC can be expected, as the anti-tumor effect of pembrolizumab is driven through immune system activation rather than through a direct interaction with tumor cells, rendering it independent of the specific

tumor type. In addition, available PK results in subjects with melanoma, NSCLC, and other solid tumor types support a lack of meaningful difference in PK exposures obtained at tested doses among tumor types.

A fixed-dose regimen will simplify the dosing regimen to be more convenient for physicians and will reduce the potential for dosing errors. A fixed dosing scheme will also reduce complexity in the logistical chain at treatment facilities and reduce wastage. The existing data suggest that 200 mg Q3W is the appropriate dose for pembrolizumab.

4.2.2.2 Rationale for the Choice of Comparator

This study will evaluate the efficacy and safety of a novel combination of a VEGFR TKI axitinib and a PD-1 immune checkpoint inhibitor pembrolizumab in treatment-naïve advanced RCC. The NCCN and ESMO recommended standard treatment in this setting includes sunitinib, pazopanib, bevacizumab plus IFN α based on highly significant results from large Phase III randomized trials. Sunitinib is the most frequently used first-line treatment in advanced RCC and has a well characterized safety profile therefore sunitinib is selected as a control for the study.

4.2.3 Rationale for Endpoints

4.2.3.1 Efficacy Endpoints

This is a pivotal Phase III randomized open-label study to evaluate the efficacy and safety of the combination of pembrolizumab plus axitinib compared with sunitinib monotherapy. The study includes dual primary efficacy endpoints: 1) PFS per RECIST 1.1 as assessed by BICR and 2) overall survival.

Progression-free survival has been used as an acceptable primary endpoint in randomized Phase III trials to support regulatory approval for new treatments in advanced RCC in both the first-line setting and in subjects who have failed prior treatments. In the first-line setting, all current approvals including sunitinib, pazopanib, and bevacizumab plus IFN α , but not temsirolimus, were based on demonstrating a statistically significant and clinically meaningful improvement in PFS without demonstrating survival benefit. Temsirolimus was approved only for the poor risk group based on demonstrating survival benefit in this subset of patients. Agents approved for subsequent treatments in advanced RCC were also based on PFS, including axitinib, sorafenib, and everolimus. Therefore, PFS is included as a primary endpoint for the study.

The primary analysis of PFS will be based on BICR in order to limit bias. Since this is an open-label study, measures have been taken to ensure that the central radiologist will be blinded to the treatment assignments of the subjects. In order to avoid PD being determined prematurely by the investigator, subjects with suspected radiologic progression first identified at the site will have all scans submitted for BICR verification of PD. The results of central PD verification will be communicated to the site promptly.

Overall survival is the ultimate gold standard endpoint to demonstrate superiority of anti-cancer therapy. Given the list of available therapies for advanced RCC for treatment beyond first-line and that the study allows subjects to select any subsequent anti-cancer treatment upon progression, the OS assessment is likely to be confounded by subsequent

treatments. The Sponsor will ensure that adequate information on subsequent therapies is collected and analyses are included to evaluate the confounding issues.

Secondary endpoints consist of ORR, DOR, and DCR per RECIST 1.1 as assessed by BICR. Durable response has been demonstrated with pembrolizumab and other immune checkpoint inhibitors in subsets of patients in multiple tumor types and provides meaningful supportive evidence for clinical efficacy.

RECIST 1.1 will be adapted to account for the unique tumor response characteristics seen with treatment of pembrolizumab. Immunotherapeutic agents such as pembrolizumab may produce antitumor effects by potentiating endogenous cancer-specific immune responses. The response patterns seen with such an approach may extend beyond the typical time course of responses seen with cytotoxic agents, and subjects may manifest a clinical response after an initial increase in tumor burden or even the appearance of new lesions. Standard RECIST 1.1 may, thus, not provide an accurate response assessment of immunotherapeutic agents such as pembrolizumab. Based on an analysis of patients with melanoma enrolled in KEYNOTE-001, 7% of evaluable patients experienced delayed or early tumor pseudoprogression. Of note, patients who had progressive disease by RECIST 1.1 but not by irRECIST had longer OS than patients with progressive disease by both criteria. Additionally, the data suggest that RECIST 1.1 may underestimate the benefit of pembrolizumab in approximately 15% of patients. These findings support the need to apply a modification to RECIST 1.1 that takes into account the unique patterns of atypical response in immunotherapy and enables treatment beyond initial radiographic progression.

irRECIST is RECIST 1.1 adapted to account for the unique tumor response seen with immuno-therapeutics as described in Nishino et al [51]. The assessment of unidimensional target lesions and response categories per irRECIST are identical to RECIST 1.1. However, Merck has implemented an adaptation related to new lesions, non-target lesions, and tumor burden assessment in order to confirm radiographic progression. irRECIST will be used by local site investigators to assess tumor response and progression, and to make treatment decisions as well as by the BICR in support of the PFS, ORR, DOR, and DCR endpoints.

4.2.3.2 Safety Endpoints

The safety objective is to characterize the safety and tolerability of pembrolizumab in combination with axitinib in subjects with advanced mRCC as a first-line treatment. The following safety parameters will be analyzed: AEs and SAEs graded per NCI CTCAE, Version 4.0 criteria with time to onset/recovery, causality and outcome; changes in laboratory values, vital signs since baseline, treatment discontinuations and reason for discontinuation, death and cause of death, etc. Concomitant medications will be collected with time and reasons for use. These are routine safety parameters collected and analyzed in Phase II/III oncology trials.

4.2.3.3 Health-related Quality of Life Endpoints

FKSI-DRS, EORTC-QLQ-C30, and EuroQol EQ-5D-3L are not pure efficacy or safety endpoints because they are affected by both disease progression and treatment tolerability.

The FKSI-DRS scale and global health status/quality of life scale from EORTC-QLQC30 are the key PRO endpoints. Although no formal hypothesis was formulated, the p-value on treatment comparisons will be provided. No multiplicity adjustment was performed.

The 9 items of the FKSI-DRS are summarized into a symptom scale ranging in score from zero (0) to thirty-six (36), with zero being the worst possible score and 36 being the best possible score [52]. The minimum important change in the FKSI-DRS used to define symptom progression is approximately a change of 2 points and that definition has been used for this mRCC symptom scale in other mRCC trials [19, 52, 53]. The Time-to-Deterioration of FKSI-DRS is defined as:

[figure not shown]
- The time to first onset of 2 or more decreases from baseline.
- The time to first onset of 2 or more decrease from baseline and confirmed by the second adjacent 2 or more decrease from baseline.
- The time to first onset of 2 or more decrease from previous nadir and confirmed by the second adjacent 2 or more decrease from nadir.

[figure not shown]
The longitudinal score changes of the EORTC QLQ-C30 global health status/quality of life scale (i.e., items 29 and 30) from baseline and the proportions of deterioration/stable/improvement at 42 weeks (i.e., based on expected median PFS of 11 months in the control group) into the study will be described. A 10-point decrease is often considered as the minimal clinical meaningful difference. Other supportive analyses include 5 functional dimensions (physical, role, emotional, cognitive, and social), 3 symptom items (fatigue, nausea/vomiting, and pain), 6 single items (dyspnea, sleep disturbance, appetite loss, constipation, diarrhea, and financial impact), and a global health and quality of life scale.

EuroQol EQ-5D-3L is another set of endpoints as a measure of health outcome. The EuroQol EQ-5D-3L will provide data for use in economic models and analyses including developing health utilities or quality-adjusted life years (QALYs).

Electronic patient-reported outcomes (PROs), in the order of FKSI-DRS, EORTC QLQ-C30 and EuroQol EQ-5D-3L, will be completed by the patient prior to all other study procedures. See the Trial Flow Chart (Section 6.0) as well as Section 7.1.2.8 for details on PRO administration and timepoints.

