3.2 Secondary Objective(s) & Hypothesis(es)

- (1) **Objective:** To compare ORR and DCR per RECIST 1.1 as assessed by BICR in subjects treated with a combination of pembrolizumab plus axitinib versus sunitinib monotherapy. DOR will also be evaluated.

Hypothesis: The combination therapy of pembrolizumab plus axitinib is superior to sunitinib monotherapy with respect to ORR as assessed by BICR per RECIST 1.1.

- (2) **Objective:** To evaluate PFS rate per RECIST 1.1 as assessed by BICR at 12, 18, and 24 months based on data adequacy; to evaluate OS rates at 12, 18, and 24 months based on data adequacy.
- (3) **Objective:** To evaluate and compare safety and tolerability profiles in subjects treated with pembrolizumab plus axitinib versus sunitinib monotherapy.
- (4) **Objective:** To compare time to deterioration (TTD) based on the Functional Assessment of Cancer Therapy Kidney Symptom Index—Disease-Related Symptoms (FKSI-DRS) scale in subjects treated with pembrolizumab plus axitinib versus sunitinib monotherapy.
- (5) **Objective:** To assess the longitudinal score changes from baseline to 42 weeks as measured by European Organization for the Research and Treatment of Cancer (EORTC) QLQ-C30 global health status/quality of life scale.

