5.2.3 Timing of Dose Administration

Study treatments should begin on the day of randomization or within 3 days of randomization in both treatment arms. Study treatments and relevant safety assessments are cycle based. The day that the first dose of study treatment is received by each subject denotes Cycle 1 Day 1 (C1D1).

For the combination arm, each treatment cycle is 21 days, which is based on a Q3W dosing schedule of pembrolizumab. C1D1 of the combination arm should start when the subject can receive the first dose of pembrolizumab. The first dose of axitinib should start on the same day when first dose of pembrolizumab is administered, if possible, or start on the following day. For the sunitinib arm, each treatment cycle is 42 days. Study treatment will continue in 21-day or 42-day cycles, for the combination arm and sunitinib arm, respectively, until study treatments are permanently discontinued for the subject. The clinical visits and assessments are detailed in Section 6 – Trial Flow Chart.

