
diagnostic quality and within the 28 day window. See Sections 7.1.2.7.1 and 7.1.2.7.2 for additional imaging requirement at baseline and follow up if RCC metastatic lesions identified outside of the standard imaging assessment anatomic regions per protocol.
 
o. Imaging after randomization will be performed at Week 12 (84 days ±7 days), then Q6W (42 days ±7 days) through Week 54, then Q12W (84 days ±7 days) thereafter until PD is BICR verified. Imaging visit window may be ± 14 days after Week 104. Unscheduled imaging can be performed as clinically indicated. The timing of imaging assessments should follow calendar days from randomization and should not be adjusted for dose delays or cycle starts. Imaging anatomic coverage should be the same as that at screening; see Section 7.1.2.7.2 for details.
 
p. Subjects who discontinue treatment for reasons other than BICR verified PD should continue with imaging assessments per the protocol defined schedule as outlined in footnote “n” until: 1) PD is BICR verified, 2) initiation of a new anti-cancer treatment, 3) death, 4) withdrawal of consent or 5) study conclusion or early termination, whichever occurs first.
 
q. Baseline bone scan is required for all subjects. If a subject has a positive baseline bone scan, after randomization, bone scans will be performed at Week 18 (Day 126 ± 7 days) and should continue to be performed Q12W (84 days ±7 days) through Week 54, subsequently Q24W (168 days ±7 days) until PD is BICR verified or further confirmed by the investigator. The timing of imaging assessments should follow calendar days from randomization and should not be adjusted for dose delays or cycle starts. Bone scans must be performed for the confirmation of Complete Response (CR) for subjects with a positive bone scan at baseline.
 
r. A brain scan will be performed during screening for subjects with brain metastasis to ensure subject is stable. After randomization, brain imaging should be performed as clinically indicated and to confirm a CR in subjects with brain metastasis at baseline.
 
s. At each clinic visit, Quality of Life (QoL) measurements should be performed before all other study procedures and assessments, including the dosing of study medication. QoL will be assessed on D1 visit of every cycle from C1-C8, D1 visit of every other cycle from C9 to C19, D1 visit of every 4 cycles from C19 (approximately Week 54) until study treatment is discontinued. In addition, QoL is to be assessed at the Treatment Discontinuation visit and 30-day Safety follow-up visit. QoL is only assessed once if these two visits are combined.
 
t. Pregnancy tests – Urine or serum β-hCG: See Section 5.1.2 for pregnancy tests requirements for screening. If the randomization pregnancy test is more than 72 hours prior to the first dose of study treatment, it should be repeated. If urine pregnancy results are positive or cannot be confirmed as negative, a serum pregnancy test performed by the local study site laboratory will be required. Pregnancy tests (serum and/or urine tests) should be repeated if required by local guidelines. Monthly pregnancy testing should be conducted as per local regulations where applicable.
 
u. PT/INR, hematology, chemistry, urinalysis, and thyroid function testing will be performed at Screening (within 10 days of randomization), on Day 1 visit of every cycle (starting from C2), End of Treatment visit and at the Safety Follow-up visit. Routine safety laboratory values of chemistry and hematology results should be available prior to each pembrolizumab dosing.
 
v. Pre-dose trough PK and ADA samples for the pembrolizumab plus axitinib arm will be collected on Day 1 of Cycles 1, 3, 5, every 4 cycles thereafter (C9D1, C13D1, C17D1, ...) and 30 days after discontinuation. Pre-dose trough samples should be drawn within 24 hours prior to pembrolizumab infusion.
 
w. Additional post-dose peak PK samples will be drawn within 30 minutes after end of pembrolizumab infusion at Cycles 1 and 9. See Section 7.1.3.3 for additional guidance for PK sampling when dosing is interrupted/delayed.
 
x. Tumor tissue from an archival tissue sample or newly obtained biopsy should be submitted at Screening for biomarker analysis.
																	

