
s. At each clinic visit, Quality of Life (QoL) measurements should be performed before all other study procedures and assessments, including the dosing of study medication. QoL will be assessed D1 and D29 visits of C1-C4; D1 visit of C5 to C10, and D1 visit of every other cycle from C10 (D1C10, D1C12) (approximately Week 54) until study treatment is discontinued. In addition, QoL is to be assessed at the Treatment Discontinuation visit and 30-day Safety Follow-up visit. QoL is only assessed once if these two visits are combined.
 
t. Pregnancy tests – Urine or Serum β-hCG: See Section 5.1.2 for pregnancy tests requirements for screening. If the randomization pregnancy test is more than 72 hours prior to the first dose of trial treatment, it should be repeated. If urine pregnancy results are positive or cannot be confirmed as negative, a serum pregnancy test performed by the local study site laboratory will be required. Pregnancy tests (serum and/or urine tests) should be repeated if required by local guidelines. Monthly pregnancy testing should be conducted as per local regulations where applicable.
 
u. PT/INR, hematology, chemistry, urinalysis and thyroid function testing will be performed at Screening (within 10 days of randomization), C1D29, C2D1, C2D29, C3D1, C3D29, Day 1 of every cycle thereafter (C4D1, C5D1, C6D1,...), the End of Treatment visit and the Safety Follow-up visit.
 
v. Tumor tissue from an archival tissue sample or newly obtained biopsy should be submitted at screening for biomarker analysis.
 
w. Samples should be collected for planned analysis of the association between genetic variants in germline/tumor DNA and drug response. If a documented law or regulation prohibits (or if the IRB/IEC does not approve) sample collection for these purposes, then such samples should not be collected at the corresponding sites. Leftover DNA extracted from planned genetic samples will be stored for Future Biomedical Research only if the subject signs the FBR consent. If the planned genetic analysis is not approved, but FBR is approved and consent is given, this sample will be collected for the purpose of FBR.
 
x. Blood for ctDNA, TCR repertoire, RNA analyses and blood for serum/plasma biomarker analyses should be collected pre-dose according to time points on the flow chart. Leftover samples may be kept for Future Biomedical Research if the subject signs the FBR consent.
																		

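### Through Week 24, the adjacent-visit rule for confirming FKSI-DRS deterioration works differently by arm, because consecutive sunitinib visits alternate between dosing and break

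*Combined protocol and SAP*

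**What the plan says.** Section 3.2 makes TTD a secondary objective, compared between the two arms: "To compare time to deterioration (TTD) based on the Functional Assessment of Cancer Therapy Kidney Symptom" (the quoted words break off inside the name of the FKSI-DRS). On inference, Section 4.2.3.3 adds: "Although no formal hypothesis was formulated, the p-value on treatment comparisons will be provided", without multiplicity adjustment.

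The same section lists three TTD definitions. The first is an unconfirmed fall of 2 or more points from baseline. The other two need confirmation:

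- The second measures the fall against baseline and reads: "The time to first onset of 2 or more decrease from baseline and confirmed by the second adjacent 2 or more decrease from baseline".
- The third uses the same adjacency rule but measures the fall against the lowest earlier score: "The time to first onset of 2 or more decrease from previous nadir and confirmed by the second adjacent 2 or more decrease from nadir".

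None is named as the main definition, and neither confirmed definition sets a minimum or maximum interval.

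The schedules come from Section 5.2.3 and footnote s of each flow chart:

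- Combination. Section 5.2.3 gives the cycle length: "For the combination arm, each treatment cycle is 21 days". The footnote in Section 6.1 gives the PRO visits: "QoL will be assessed on D1 visit of every cycle from C1-C8, D1 visit of every other cycle from C9 to C19". After that they come every fourth cycle.
- Sunitinib. Section 5.2.3 gives the cycle length: "For the sunitinib arm, each treatment cycle is 42 days". The footnote in Section 6.2 gives the PRO visits: "QoL will be assessed D1 and D29 visits of C1-C4; D1 visit of C5 to C10". After that they come every other cycle. The flow chart in Section 6.2 places dosing on D1 to D28 and the break on D29 to D42.

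Section 8.0 defers the PRO analysis plan to a supplemental SAP (sSAP), which is not among the documents reviewed.

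**The concern.** A confirmation rule is meant to ask the same question of everyone: did the fall persist? With no interval stated, the next scheduled visit decides what persistence means. In the combination arm that visit comes 3 weeks later on continuous axitinib. On sunitinib it comes at the opposite phase of the dosing cycle.

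Section 4.2.3.3 itself says that these scales respond to treatment tolerability as well as to progression, and the items in Section 7.1.2.8.1 include energy and fatigue. A tolerability-driven fall at D29 that lifts above the threshold by the next D1 is discarded. An equal fall on continuous treatment is kept. Confirmed TTD would then look longer on sunitinib for a reason unrelated to the size of its on-drug effect. What is at stake is the reading of one secondary PRO comparison; the primary endpoints are unaffected.

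**Working it through.** **Step 1. Calendar.** Day of visit = (cycle − 1) × cycle length, plus 28 for a D29 visit.

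Check against the plan's own figure: both footnotes put the switch to sparse assessment at about Week 54. Combination C19 D1 = 18 × 21 = 378 days = Week 54. Sunitinib C10 D1 = 9 × 42 = 378 days = Week 54. Both agree.

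**Step 2. Gap to the next assessment.**

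| Period | Combination | Sunitinib |
|---|---|---|
| Visits to Week 24 | Weeks 3, 6, 9, 12, 15, 18, 21, 24 | Weeks 4, 6, 10, 12, 16, 18, 22, 24 |
| Gaps to Week 24 | 3 weeks, eight times | 4 and 2 weeks in turn, four times each |
| Weeks 24 to 54 | 6 weeks | 6 weeks |
| After Week 54 | 12 weeks | 12 weeks |

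Both arms have 8 post-baseline assessments to Week 24, with a mean gap of 24 / 8 = 3.0 weeks. The difference is therefore not one of density. It is that the sunitinib 4-week gap (D1 to D29) runs over dosing and the 2-week gap (D29 to next D1) runs over the break, so consecutive visits always sit at opposite phases.

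**Step 3. Does unequal spacing alone matter?** Take a stationary, serially correlated score with an assumed SD of 2 to 3 points and a correlation time of 30 to 90 days, and no drug cycle. The chance that a fall is confirmed at the next visit is 0.65 to 0.75 on the combination. On sunitinib it is 0.70 to 0.79 after a D29 fall and 0.62 to 0.72 after a D1 fall. The cumulative chance of confirmed deterioration to Week 24 differs by only about 1 percentage point between arms.

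Add an assumed 1 to 2 point dip at D29 that resolves off drug. Confirmation on sunitinib becomes 0.41 to 0.67 after a D29 fall and 0.76 to 0.96 after a D1 fall. Dosing phase, not spacing, drives confirmation.

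**Step 4. Size with equal on-drug effect in both arms.** Illustrative simulation of the from-baseline definition, 100,000 subjects per arm. Change from baseline = phase mean + subject effect (SD 2) + visit noise − baseline noise (noise SD 1 to 2), with threshold −2. Onset is counted through Week 18, plus the confirming visit. None of these SDs or means is in the documents.

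| Mean change on drug / in break | Gap in proportion confirmed, combination minus sunitinib |
|---|---|
| −2 / −2 (no easing) | about 0 |
| −2 / −1 | about 7 to 11 points |
| −2 / 0 | about 17 to 25 points |
| −3 / 0 | about 27 to 41 points |

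In the −2 / −1 case, 56 to 59% are confirmed on the combination and 45 to 52% on sunitinib: 56 − 45 = 11 and 59 − 52 = 7.

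**Step 5. What is due to adjacency?** On the same simulated visits the unconfirmed definition shows gaps of 4 to 8 points, because half of the early sunitinib visits fall off drug. Confirming at the first visit at least 5 weeks later leaves 5 to 9 points. The larger gaps in Step 4 therefore come mostly from the adjacency rule. In the mildest case the 5-week rule removes at most 7 − 5 = 2 to 11 − 5 = 6 points.

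**The case against.** The strongest reply is that this is a choice of estimand. Confirmation is there to ask whether a fall persists, and one that has gone at the next assessment did not. The unconfirmed definition is listed first and has no adjacency rule, so the plan already offers a result free of it. TTD carries no formal hypothesis and no controlled alpha. Any distortion is conservative for the experimental arm. The unseen sSAP may already set an interval, and figures are missing around the list of definitions.

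Most of that stands as a limit on importance. It does not remove the point: as written, persistence means 3 weeks on continuous drug in one arm and survival of a phase change in the other, and the two arms are compared with a p-value.

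Several stronger readings are tempting and are not supported:

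- A reader might infer that the rule biases the comparison by itself. With no on/off swing the gap is about 0, and the documents give no swing.
- A reader might infer that cyclic falls on sunitinib can never be confirmed. That needs recovery above the threshold at each D1; with a 1-point swing, 45 to 52% are still confirmed.
- A reader might infer that both sunitinib gaps cross the break, or that the arms differ throughout. Only the 2-week gap crosses it, and the intervals match after Week 24.
- A reader might infer that the adjacent rule should simply be replaced. A 5-week rule skips the visit between, so a fall, a recovery and a second fall counts as confirmed. With off-drug change 0, that newly confirms about 13 to 36% of sunitinib subjects, against 3 to 6% on the combination.

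**Conclusion.** The point holds for the two confirmed definitions and for Weeks 0 to 24 only. The structural part is certain: it follows from footnote s in Sections 6.1 and 6.2 and the cycle lengths. The direction, against the experimental arm, assumes equal on-drug falls in both arms and easing in the break that crosses the 2-point threshold.

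The size rests on assumed values. Swings of 1 to 3 points give gaps of about 7 to 41 percentage points in the proportion confirmed. That is a proportion, not a time or a hazard ratio, and it was worked for the from-baseline definition, not the nadir one. After Week 24 confirmation changes with time on study (6, then 12 weeks) but equally in both arms. This is a minor, inexpensive point about interpreting a secondary PRO endpoint.

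**What to change.** In the sSAP, keep the adjacent-visit rule as stated. Beside it, for both confirmed definitions, pre-specify a phase-matched version that confirms at the first nominal scheduled assessment at least 5 weeks after the first fall. Interpret the confirmed TTD comparison in light of both.

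On the existing schedule the added version gives a 6-week interval in both arms through Week 54, pairing D29 with D29 and D1 with D1, with two exceptions. A Week 21 fall on the combination confirms at Week 30 (30 − 21 = 9 weeks). A Week 22 fall on sunitinib also confirms at Week 30 (30 − 22 = 8 weeks), and that pair is D29 against D1, because D29 assessments stop after C4.

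Apply the 5 weeks to nominal visit weeks. With the ±7-day PRO window in Section 7.1.2.8, two visits a nominal 42 days apart can be 42 − 14 = 28 days apart and would fail a rule based on actual dates.

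The cost is sSAP wording; no new assessments are needed. There are two downsides. The added version ignores an intervening recovery, which is why it should sit beside the stated rule. It also cannot confirm a fall when PRO completion stops within about 5 weeks of it, so a few early falls are lost in each arm. If the sSAP already fixes a confirmation interval, that rule should be checked against the same visit grid.
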